## 1. INTRODUCTION:

Herbal medicines have been in use for millennia. In recent years, there has been increasing interest in herbal medicines as they have increased in popularity in the developed world. The use of self-prescribed herbal medicines in USA increased from 2.5 to 12.1% between 1990 and 1997 and frequency of consultations with practitioners of herbal medicine rose from 10.2 to 15.1% (1). A similar increase has been reported in Europe (2). The justification for using these remedies appears to be based on traditional use rather than evidence from clinical trials.

Many herbal preparations are used in the treatment of diabetes mellitus in Sri Lanka. As in Europe, many patients use them concurrently with prescribed medication but do not tell their doctor about it (3). There is anecdotal evidence of such patients showing improved control and even an increased incidence of hypoglycemia in such patients. There is some evidence from animal studies and non-randomized uncontrolled studies in humans for the efficacy of some of these remedies (4).

The alpha glucosidase inhibitor acarbose is used in clinical practice (5). An alpha glucosidase inhibitor kotalanol has been identified in one commonly used herb, *Salacia reticulata* called Kothala Himbutu in Sinhalese by traditional physicians (6). Data on the efficacy of the herbal preparation from randomized controlled clinical trials is not available. Traditionally this preparation is ingested as an herbal tea (Kothala Himbutu tea), where the herbal mixture is ingested in a cup of boiled water and in the form of a tea bag prepared using a formula passed on in an oral tradition to members of the family of the Ayurvedic physician. Efficacy of tea bags containing *Salacia reticulata* in lowering blood glucose in people with type 2 diabetes and its safety in a double blind randomized cross over trial was demonstrated in 2006 (7). Recently biscuit containing extract of *Salacia reticulata* (Kothala Himbutu biscuit) was tested and found to have low glycaemic index compared to a biscuit not containing *Salacia reticulata* (8). This biscuit is available in the market in Sri Lanka and consumed by customers.

## 2. OBJECTIVE:

We intend to conduct a triple blind randomized clinical trial to investigate the effect of a biscuit containing the extract of *Salacia reticulata* on the fasting blood glucose levels and

HbA1c in patients with Type 2 diabetes mellitus and also to find out whether there are any side effects on other vital organs such as kidneys and liver.

#### 3a. Selection criteria:

Male and female patients who have been diagnosed as having Type 2 diabetes mellitus for a minimum period of 6 months, who are interested in seeking Ayurvedic treatment as sole treatment or as complimentary treatment to western medical treatment and meet the following criteria will be selected to participate in this study.

1. Onset of diabetes mellitus for six months.
2. Aged between 30 and 65 years
3. Stable glycaemic control over the preceding 2-3 months. They will be initially selected from a range of HbA1c varying from 7 – 14 and the individual subject should not have a variation of >20% between the previous HbA1c and the HbA1c done at the commencement of the study

#### 3b. Exclusion Criteria:

The following patients will be excluded from the study.

#### Exclusion Criteria:

1. Chronic kidney disease with estimated Glomerular filtration rate less than 30ml/hour
2. Severe valvular heart disease or heart failure.
3. Those on Insulin therapy
4. Severe liver disease (AST > 10 X times the upper limit)

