### 4. RECRUITMENT

Patients who seek treatment for diabetes mellitus will be screened for participation in the study. The subjects will be provided with a detailed patient information sheet supplemented by a verbal explanation and reviewed at a later date to obtain written consent in order to give them an opportunity to discuss their participation with family and other relevant persons whose advice is deemed of value by the subject.

Type I Diabetes will be excluded by clinically. Participant will have two HBA1C within the two months period to ensure stability of glycemic level. This is done to exclude recruiting patients who have rapidly changing glycaemic values. As this trial is a crossover trial stability of the glycemic control over time needs to be assured to prevent excessive variation of HBA1C interfering with study outcome. A medical officer will perform a complete history and clinical examination with blood pressure. Blood and urine samples will be tested for baseline investigations such as FBC, UFR, LFT, CRP, renal & liver profiles.

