#### 4a Primary outcome variable

- I. Glycaemic control evaluated with HBA1C carried out centrally with ion exchange HPLC and the units will be NGSP standard.
- II. Serious liver and kidney adverse events when taking the biscuits containing the extract of *Salacia reticulata*.

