##### 8 a. Visit Schedule

##### V1 - Selecting patients and Recruitment

- Check for inclusion and exclusion criteria
- Informed written consent form signed
- Obtain demographic data
- History and examination
- Dietary advice
- Screening investigations
  - FBC, liver profile, renal profile, FBS, HbA1c, ECG, Urine for microalbumin
- V2 - 8 weeks after V1
  - Review investigation reports of V1 in relevance with exclusion criteria
  - 2nd HbA1c, Lipid profile, UFR
- V3 Trace laboratory reports
  - Provision of a glucometer
  - Glucometer Training and self-monitoring of blood glucose
- V4 Randomization
  - Checking for glucometer capability
  - Review the blood sugar series
  - History and examination
  - Providing biscuit
- V5 - May be over the phone (1 week after providing biscuit)
  - Evaluate the compliance for the biscuit
- V6 - 1month after providing biscuit
  - Evaluate the blood sugar series
  - History and examination
  - Review dosage of other drugs
  - Provide stock of biscuit for 1 month
  - SGPT, SGOT, Serum creatinine
- V7 - 2months after providing biscuit
  - Evaluate the blood sugar series
  - Trace laboratory reports
  - History and examination
  - Review dosage of other drugs
  - Provide stock of biscuit for 1 month
  - SGPT, SGOT, Serum creatinine
- V8 - 3 months after providing biscuit
  - Stop biscuits

History and examination  
Trace the laboratory reports  
Review dosage of other drugs  
SGPT, SGOT, Serum creatinine, HbA1c, FBS, Urine for microalbumin  
1 month washout period

V9 - 1 month after stopping biscuits  
Evaluate the blood sugar series  
History and examination  
Trace the laboratory reports  
Review dosage of other drugs  
Change to other group of biscuit (provide biscuit for 1 month)  
SGPT, SGOT, Serum creatinine

V10 1 month after changing biscuits  
Evaluate the blood sugar series  
History and examination  
Trace laboratory reports  
Review the dosage of other drugs  
SGPT, SGOT, Serum creatinine  
Provide stock of biscuit for 1 month

V11 2 month after changing biscuits  
Evaluate the blood sugar series  
History and examination  
Trace laboratory reports  
Review dosage of other drugs  
SGPT, SGOT, Serum creatinine  
Provide stock of biscuit for 1 month

V12 3 month after changing biscuits  
History and examination  
Trace laboratory reports  
Review dosage of other drugs  
SGPT, SGOT, Serum creatinine, HbA1c, FBS, Urine for microalbumin

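### The only numeric kidney limit for entry is an eGFR below 30 ml per hour, which is 0.5 ml per minute and cannot work as a screening threshold

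*Combined protocol and SAP*

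**What the plan says.** Section 3b of the combined protocol and SAP lists four exclusion criteria. Two of them contain a laboratory number. Criterion 1, for the kidney, reads "Chronic kidney disease with estimated Glomerular filtration rate less than 30ml/hour". Criterion 4, for the liver, reads "Severe liver disease (AST > 10 X times the upper limit" and is expressed as a multiple of the upper limit.

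The criteria are applied before randomization. The visit schedule (section 8 a) has staff check inclusion and exclusion criteria at V1. At V2, eight weeks later, they are to "Review investigation reports of V1 in relevance with exclusion criteria". Randomization follows at V4.

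The kidney-related tests before V4 are:

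- at V1, a renal profile (in "FBC, liver profile, renal profile, FBS") and urine microalbumin (in "ECG, Urine for microalbumin");
- at V2, a UFR (in "Lipid profile, UFR").

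Section 4 describes the baseline work-up in similar terms: "Blood and urine samples will be tested for baseline investigations such as FBC, UFR, LFT, CRP, renal & liver profiles". It also requires a full history and examination by a medical officer. None of these entries states a cut-off.

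Section 4a names as a primary outcome "Serious liver and kidney adverse events when taking the biscuits containing the extract of" the study herb.

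**The concern.** An entry criterion should be usable exactly as written. The number 30 is attached here to a rate per hour, whereas eGFR is ordinarily reported per minute. That convention is general knowledge; the documents do not state it. The choice of time unit moves the limit by a factor of 60, and the literal limit is so low that the criterion would stop doing its job.

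Two things would be at stake. First, staff checking V1 results against the criteria must either apply a limit that screens out almost no one or substitute their own reading of an eligibility rule. Second, kidney safety is part of the objective and of the primary outcome. Participants' safety, and a reader's understanding of whom the kidney safety results describe, both depend on a clear statement of which patients were kept out for poor kidney function.

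**Working it through.** The plan derives no figure here, so there is no calculation of its own to reproduce. The check is a unit conversion followed by a search for any text that would repair the criterion.

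**Input.** Limit as written in section 3b, criterion 1: eGFR below 30 ml/hour.

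**Conversion.**

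- Per minute: 30 ml/hour ÷ 60 min/hour = 0.5 ml/min.
- Per day: 30 ml/hour × 24 hours = 720 ml/day.
- Ratio between a per-hour and a per-minute reading of the same number: 60.

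**Search for a repairing statement.**

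| Place | Kidney content | Numeric limit |
|---|---|---|
| Section 3b, criterion 1 | eGFR | yes, in ml/hour |
| Section 4, Recruitment | renal profile, UFR | none |
| Section 8 a, V1 | renal profile, urine microalbumin | none |
| Section 8 a, V2 | UFR | none |

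The supplied text therefore contains one numeric kidney entry limit. There are three distinct kidney-related tests before randomization (renal profile, urine microalbumin, and UFR, taking UFR to be a urine test), and none of the three has a stated limit. The supplied text gives no eGFR equation and no second statement of the limit in another unit. The renal profile is not itemised, so it may include creatinine; serum creatinine is first named explicitly at V6, one month after biscuits are provided.

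**Role of the other tests.** The V2 step compares V1 reports with the exclusion criteria. For kidney function, the only number available for that comparison is the one in criterion 1. The tests supply results to judge but no alternative rule to judge them by.

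**Patients affected.** This cannot be computed. It would need the eGFR distribution of the clinic population, which the documents do not give. That the literal limit excludes essentially no one is an assumption based on how far 0.5 ml/min lies from any plausible clinic value.

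**The case against.** The strongest reply is that this is an obvious typographical slip with no demonstrated consequence. The criterion names chronic kidney disease as well as a number. A medical officer takes a history and examines each patient, and renal results are reviewed before randomization. Harm requires someone to apply 0.5 ml/min without noticing, and nothing in the documents suggests that would happen.

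Monitoring after randomization is also substantial. Serum creatinine is scheduled at all seven visits from V6 to V12, and urine microalbumin at V8 and V12. All adverse events are recorded, and a data and safety monitoring board is planned. Because each patient is planned to receive both products, a looser entry rule would not by itself unbalance the comparison. On this view the point is editorial, and it is a unit error rather than a wrong calculation.

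Most of this stands. The slip is probably recognisable, the practical effect may be small, no bias follows, and the error is one of units. What does not follow is that the text can be left alone. Monitoring after randomization does not decide who is randomized. The checks before randomization refer back to the criterion and have no limit of their own. The documents do not state the intended unit anywhere else, so staff who notice the slip must still guess at the rule.

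**Conclusion.** The concern holds. As written, the only numeric kidney entry limit is 0.5 ml/min (720 ml/day), and nothing else in the supplied text corrects it. Followed literally, it would not screen patients on kidney function. It should be fixed because it is an operative eligibility rule in a trial with a primary kidney safety outcome.

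The conclusion rests on two things from outside the documents: general knowledge of how eGFR is expressed, and the assumption that essentially no clinic patient has a value below the literal limit. It is also confined to the supplied text, from which some material was removed before review. The number of patients affected is unknown. The treatment comparison, sample size and planned analysis are not affected.

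**What to change.** The sponsor should correct the unit in exclusion criterion 1 and confirm the value it intends. The corrected wording should then be used wherever eligibility is recorded, including the material staff use for the V1 and V2 checks. The choice of threshold belongs to the sponsor, and none is suggested here.

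The cost is a one-line protocol correction, with no change to the design, sample size or analysis.

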### 4. RECRUITMENT

Patients who seek treatment for diabetes mellitus will be screened for participation in the study. The subjects will be provided with a detailed patient information sheet supplemented by a verbal explanation and reviewed at a later date to obtain written consent in order to give them an opportunity to discuss their participation with family and other relevant persons whose advice is deemed of value by the subject.

Type I Diabetes will be excluded by clinically. Participant will have two HBA1C within the two months period to ensure stability of glycemic level. This is done to exclude recruiting patients who have rapidly changing glycaemic values. As this trial is a crossover trial stability of the glycemic control over time needs to be assured to prevent excessive variation of HBA1C interfering with study outcome. A medical officer will perform a complete history and clinical examination with blood pressure. Blood and urine samples will be tested for baseline investigations such as FBC, UFR, LFT, CRP, renal & liver profiles.

#### 4a Primary outcome variable

- I. Glycaemic control evaluated with HBA1C carried out centrally with ion exchange HPLC and the units will be NGSP standard.
- II. Serious liver and kidney adverse events when taking the biscuits containing the extract of *Salacia reticulata*.

#### 4b Secondary outcome variable

Fasting blood glucose measured by glucose oxidase method.

### 5. THE STUDY PRODUCT

A biscuit containing the extract of *Salacia reticulata* is the active treatment. The study product is available in the market. Both study biscuit containing *Salacia reticulata* and the placebo will be wrapped in identical covers for concealment.

1. To ensure the uniformity of the product between successive batches, Ceylon Biscuits Ltd (CBL) adheres to strict quality control measures during the production process and prior to release of the product to the market.
2. Formulation of the biscuit (study product): By CBL.
  - a. Placebo biscuit & formulation: - A biscuit identical to the study product, without the extract of *Salacia reticulata*. The fiber content of the biscuit containing Kothala himbutu extract and the placebo will be identical.
  - b. Contents of the study biscuit

Name of ingredient	Quantity (As %)
Wheat flour	73.51
Yeast	1.06
Vegetable fat	12.82
Wheat bran	8.12
Leavening agents	0.82
Salt	1.48

Soya lecithin	0.15
Water extract of Kothala himbutu	

## 6. SAMPLE SIZE & RANDOMIZATION

1. Consecutive patients who seek treatment for diabetes mellitus will be screened for eligibility.
2. Those who are eligible will be invited for the study.
3. Sample size calculation:

Sample size was initially calculated by using a formula specific for crossover studies (9). The standard deviation (0.9) to calculate the standard error was taken from the baseline data (7). Clinically significant improvement of HbA1c in the intervention group over the placebo group was estimated as 0.5 units of HbA1c (difference in means). As this gave very low sample size (13 in each arm) we calculated the sample size for parallel studies according to Pocock (10). Significance level (alpha) 0.05 and power (1-beta) = 0.8 giving rise total of 51 patients were in each arm. With anticipated dropout rate of 10%, 112 patients were estimated sample size for a single center study

### 6b Randomization

[name] will generate randomization code (A or B) using a computer and prepared sealed, serially numbered, opaque envelopes. All eligible participants will be identified and given a serial number on the day of randomization (after run-in period). A study assistant will open the envelope and assign the patient to either biscuit A (placebo) or B (KH) and deliver the biscuit boxes to the patient. The manufacturers (Ceylon Biscuits Ltd) held randomization code.

### 6C. Allocation concealment

Investigators, patients and those assessing the analysis will be masked to the group outcome. Both Kothala Himbutu (KH) and placebo biscuits are identical in size, wrapped in same cover, and packed in identical boxes.

Patients participating in the trial will be asked about prior consumption of KH biscuits bought from the market (to exclude contamination). At the end of each period patients were asked whether they could assume the type of biscuit (KH biscuit or placebo) given to them and their preference for the type.

## 7. STATISTICAL ANALYSIS (10)

1. Being a cross over trial, the analysis will be done as a paired analysis.
2. Intention to treat analysis.

3. Formal tests for period effect, treatment effect, carryover effect and interaction between treatment and period will be carried out.

#### 8. PROCESS OF THE TRIAL

After running period where stability of HBA1C is assured patients will be randomized to receive either a standard preparation of Kothala himbutu biscuits or a placebo, a similar biscuit without the extract of *Salacia reticulata*. The study product and the placebo will be given to the participants and the investigators and the participants will be blinded to the treatment.

Four biscuits will be taken as a mid morning and afternoon snack, at 10am and 4 pm respectively. Oral hypoglycemic treatment for diabetes taken at the time of recruitment will be continued but subject to change if the condition of the patient changes, as determined by treating clinician.

Patients will continue treatment for a period of seven months separated by a washout period of one month at cross over. On completion of the first three months on either treatment or placebo patients will not receive either placebo or biscuit with the active ingredient during a wash out period of one month. The wash out period is determined as one month to minimize the carry over bias. In the event that significant difference exists between the two groups at the end of three months, the study will be terminated at that point.

During this time the subjects will have a minimum of eight to ten visits inclusive of the booking visit and will meet with a medical officer at each visit for review of glycaemic control and other possible complications. A six-point blood glucose profile (pre and post breakfast, pre and post lunch, pre and post dinner samples) will be performed on one day during the week prior to each visit.

HBA1C will be performed at recruitment, at three months and on completion of the study at seven months. Existing oral medication and doses for diabetes mellitus will be adjusted as requested during the study.

In the event that the clinical investigators feel that significant deterioration of glycaemic control has occurred or that the patient would require a step up to insulin, patients will be withdrawn from the study.

Specific written instructions will be provided for the timing of snacks in the standard dosage. Counting the unused biscuits will assess compliance. All adverse events will be recorded. Patient preference for the biscuits will also be assessed.

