#### 10. DATA ANALYSIS AND PRESENTATION:

There will be interim analysis of data after the end of first treatment period. to observe the progress of each patient to ensure good glycaemic control. Standard statistical packages will be used in data analysis. Patient flow will be presented in a CONSORT diagram.

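### The month-3 termination rule is undefined and has no error control; if it means HbA1c tested at 0.05, the overall type I error is about 9% and the trial would probably stop before the planned crossover analysis

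*Combined protocol and SAP*

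**What the plan says.** - **Section 8, Process of the Trial.** The trial ends after the first treatment period if a "significant difference exists between the two groups at the end of three months, the study will be terminated at that point". The wording is mandatory. HbA1c is measured at recruitment, month 3 and month 7, so a between-group HbA1c comparison at month 3 is possible.
- **Section 10, Data Analysis and Presentation.** "There will be interim analysis of data after the end of first treatment period", with the stated aim "to observe the progress of each patient to ensure good glycaemic control". Termination is not mentioned.
- **Section 6, Sample Size & Randomization.** The crossover formula gave 13 per arm, and the parallel-group formula was used instead: "Significance level (alpha) 0.05 and power (1-beta) = 0.8 giving rise total of 51 patients were in each arm". This is the only significance level given. Entry is staggered: "Consecutive patients who seek treatment for diabetes mellitus will be screened for eligibility".
- **Section 7, Statistical Analysis.** "Being a cross over trial, the analysis will be done as a paired analysis", and also "Formal tests for period effect, treatment effect, carryover effect and interaction between treatment and period will be carried out". Nothing is said about an earlier look.
- **Section 4a.** Both HbA1c and serious liver and kidney adverse events are listed as primary.
- **Section 8a, Data monitoring & Safety Board.** An independent board reviews interim data regularly. No boundary or stopping authority is given.

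**The concern.** The plan gives itself two chances to declare a difference, a parallel-group comparison at month 3 and the paired analysis at month 7, and does not divide the error between them. Because the rule names no outcome, test or level, those choices could be made after the data are seen. With two primary outcomes of different kinds, it is not even clear whether the rule is for efficacy, harm or both.

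The sample size makes this more serious. The trial is sized so that a parallel-group comparison has 80% power, and the month-3 comparison is exactly that. If the planning assumptions are right, an efficacy reading of the rule means the trial probably ends before it becomes a crossover. Patients enter consecutively, so some may already have crossed over when the last reach month 3, and the plan does not say how the rule treats them.

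**Working it through.** **Inputs.** From Section 6: difference 0.5, SD 0.9, alpha 0.05, power 0.8, 51 per arm. Assumed: two-sided 0.05 on HbA1c at both looks, and one look once all patients reach month 3. The within-patient correlation ρ is not given, so a range is shown.

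**The plan's own figures.**
- Parallel: 2 × (0.9 × (1.960 + 0.842) / 0.5)² = 50.9, so 51 per arm. Then 102 × 1.1 = 112.2, which gives the stated 112. A one-sided test would need 41, so the plan's 0.05 is two-sided.
- Crossover: (0.9 × 2.802 / 0.5)² = 25.4, so 26 in total or 13 per arm, with 0.9 used as the SD of within-patient differences. Using 0.9 as the single-measurement SD as well implies 0.9² = 2 × 0.9² × (1 − ρ), so ρ = 0.5.

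**Overall type I error.** The month-3 contrast has variance 2σ²/n and the AB/BA contrast has σ²(1 − ρ)/n. Their covariance is σ²(1 − ρ)/n, so their correlation is √((1 − ρ)/2). The overall error is P(|Z1| > 1.96 or |Z2| > 1.96) under that bivariate normal:

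| ρ | Correlation of the two tests | Overall type I error |
|---|---|---|
| 0 | 0.707 | 8.3% |
| 0.3 | 0.592 | 8.8% |
| 0.5 | 0.500 | 9.1% |
| 0.7 | 0.387 | 9.4% |
| 0.8 | 0.316 | 9.5% |
| 0.9 | 0.224 | 9.6% |

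The ceiling is 1 − 0.95² = 9.75%. A t-test simulation (51 per sequence, 20,000 runs, no effect) gave 8.3%, 9.2% and 9.6% at ρ = 0, 0.5 and 0.8.

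**Chance of stopping at month 3.** The standard error is 0.9 × √(2/51) = 0.178, so a stop needs an observed difference beyond 1.96 × 0.178 = 0.35. At a true 0.5 the standardised effect is 0.5 / 0.178 = 2.805, and P(Z > 1.960 − 2.805) = 80%.

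| True effect | SD | P(stop) | Mean estimate given a stop |
|---|---|---|---|
| 0.5 | 0.9 | 80% | 0.56 |
| 0.4 | 0.9 | 61% | 0.51 |
| 0.25 | 0.9 | 29% | 0.46 |
| 0 | 0.9 | 5% | – |
| 0.5 | 1.2 | 56% | – |
| 0.5 | 1.5 | 39% | – |

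The t-test values are within one percentage point of these. The larger SDs are assumptions: the 0.9 comes from another study's baseline data, and this trial admits HbA1c from 7 to 14. The last column is the mean of the truncated normal; simulation agrees to 0.002.

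**Precision.** The standard error is 0.178 at month 3. For the completed crossover it is 0.9 × √((1 − ρ)/51): 0.126, 0.089 or 0.056 at ρ = 0, 0.5 or 0.8.

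**Alternative boundaries.**
- Interim 0.001 and final 0.05: overall error 0.0502 (ρ = 0) to 0.0509 (ρ = 0.9). The interim critical value is 3.291, so stopping at the planning effect is P(Z > 3.291 − 2.805) = 31% (29% by t-test).
- Equal levels at both looks: 0.029, 0.027 or 0.026 at ρ = 0, 0.5 or 0.8. At 0.027 the trial still stops with probability P(Z > 2.21 − 2.805) = 72%.

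**The case against.** **The word may not mean p < 0.05.** Section 8 also uses it for a clinical judgement of deterioration, and Section 6 calls 0.5 units clinically significant. If the rule means an observed difference of at least 0.5, the false-stop rate is P(|Z| > 2.805) = 0.5%, the overall error is about 5.2% to 5.4% (ρ from 0 to 0.8), and stopping at the planning effect is about 50%. If the rule covers harm only, neither the 9% nor the 80% applies. This stands: both figures belong to one reading. It does not rescue the rule, because the plan does not say which reading is meant. Even on the 0.5 reading, the crossover is lost about half the time when the planning effect is real.

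**The 80% could also be higher.** It is 84% with all 56 per arm evaluable. It is 94% with 80 per arm, since Section 3 also gives a total of one hundred and sixty. With a baseline-adjusted test it is about 90% at ρ = 0.5 and 98% at ρ = 0.7. This also stands. With the larger SDs, the spread is roughly 39% to 98%; 80% is what the plan's own inputs give.

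**The precision loss is a worst case.** It assumes no second-period data at the stop, and with slow enrolment some patients would have finished both periods. A stop at 51 per arm also has the precision the plan was sized for. Both points are fair, but partial second-period data do not allow the Section 7 analyses as planned.

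**Part of the Trial Monitoring section was not available.** The statement that nothing defines the rule or adjusts for it applies to the available text. Sections 8 and 10 would need reconciling in any case.

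**Conclusion.** The concern holds and must be fixed. That the rule is undefined, unadjusted and unreconciled with Section 10 follows from the available text without any assumption. The size is conditional. With HbA1c tested at two-sided 0.05 at both looks, the overall type I error is about 9% against the stated 5%, and it lies between 8.3% and 9.75% for any ρ from 0 to 1. Under the same condition, with one look at 51 per arm, SD 0.9 and an unadjusted comparison, a true difference of 0.5 would stop the trial about 80% of the time. The upward bias after a stop is modest at the planning effect and larger at smaller effects. Additional board looks, or testing more than one outcome at month 3, would raise the error further.

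**What to change.** First clarify whether the sentence in Section 8 was meant to cover harm. If so, state that provision separately; nothing here removes it.

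For efficacy, the preferred wording is that there is no stop: all patients cross over, and the board's month-3 review is for safety and conduct. This keeps the Section 7 analysis and the 0.05 level intact.

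If an efficacy stop is kept, Section 8 should name HbA1c as the outcome, specify the test and its sidedness, give the decision to the monitoring board, say how patients who have already crossed over are handled, and set a stringent boundary. One option is p < 0.001 at month 3 with 0.05 at the end (overall about 0.051). Equal levels of about 0.027 also control the error, but would still end the trial about 72% of the time at the planning effect.

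Section 10 should state the same purpose and rule as Section 8.

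**Cost.** Protocol wording only, with no extra patients or visits. Without the stop, a real effect is reported about four months later (month 7 rather than month 3). With the 0.001 boundary, early stopping at the planning effect falls from about 80% to about 31%, but the rarer stops carry more bias: the mean estimate given a stop is 0.5 + 0.178 × φ(0.485)/0.314 = 0.70, where φ(0.485) = 0.355 is the standard normal density.
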